To achieve the aim of this study we will conduct a randomized controlled trial with three arms during May-Dec 2017. Participants will be Danish adults traveling on vacation in 2018 for a period of 1-3 weeks, recruited from the civil registration system. After enrollment and pretesting, participants will be randomly assigned to one of three experimental conditions. Three experimental groups will receive innovative intervention strategies for promoting sun protection practices during vacation – Protection Routine (1), Protection Routine (2) or both Protection Routine (1+2). The fourth experimental condition will be a minimal treatment control group. The primary outcomes of the trial will be a reduction in frequency of sunburn by adherence to the current sun protection advice from the Danish Cancer Society, i.e., use of shade, hats, protective clothing, and sunscreen as secondary outcomes. We hypothesize that the following two interventions will be able to reduce significantly the UVR exposure and risk of sunburns in Danes going on vacation to destinations with high UVI.

Protection routine 1

The existing evidence of sun protection against the detrimental effect of UV radiation shows that it is effective if performed correctly [26, 28]. We will develop a package of existing training and information and test if it will lead to better adherence. The package will include:

- The rationale of the prioritized sun advice [32]
- Activity planner, with suggestions to why a break from the sun is beneficial and how to plan activities before and after UVI maximum i.e. morning/early noon and afternoon/evening [32]
- Download of the UV-application ‘UVindeks’ for smartphones developed by the campaign and activating UV alert of geographic destination [33]
- A skin type guide

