- A newly developed instruction for correct application of sunscreen [40]

Denmark is not a hat-wearing society. By making smart design hats available and attractive may increase this sun protection behavior, which has large potential in prevention of skin cancer (**ibid: p2**). A very simple study showed that a brief instruction to sunscreen application increased the provided protection significantly [40].

Protection routine 1+2

The group will receive both above mentioned interventions and will reveal potential dose response effects from level of protection.

Control group

All groups including the control group will receive a minimal intervention with the current sun advice from the Danish Sun Safety Campaign.

Study population

The participants of the study are recruited from the Danish civil registration based system. The study population will represent all groups of the Danish population. Eligibility criteria for the project are persons living in Denmark going on vacation in May-December 2018 and having a smartphone compatible with either apple iOS (version 7.0 or newer) or Google Android (version 4.0 or newer). The period May to December is chosen as it includes all types of vacationers. The summer vacation constitutes the majority of the sunny vacations of the Danes. The period includes both the summer, where Danes typically travel to the Mediterranean area and the winter period where travel patterns change a bit to more exotic areas like Thailand, Egypt and the Canarias Islands. Exclusion criteria are persons younger than 18 years of age.

Randomization

The participants will be randomized to one of the intervention groups or to the minimal-treatment control group. The randomization procedure is described in the protocol.

Confounders

Possible confounders includes age, gender, education, skin type, skin cancer history, nevi, sun-seeking behavior and number of sunny vacations in past 5 years [28].

Statistical methods and power calculations

The number of completing participants (n= 1.980) is based on a power calculation, recruitment for similar studies conducted by the applicant [41, 42] and our recent pilot study (unpublished, summarized in the end of this application).

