A statistical power calculation shows that this sample size yields 95 % probability to detect a 10-percentage point drop from 50 % to 40 % in sunburn between an intervention group and the control group, and 80 % probability to detect a 7-percentage point drop from 50 % to 43 %. Our pilot study showed a 17-percentage point difference between our participants (32 %) relative to our annual sun surveys (49%). The number of invited participants to reach a final sample of ~2000 are included in the flow diagram in the protocol.

To obtain the final study sample size, we assumed 25 % of Danes invited to participate will volunteer for the project [41], >80 % will use of interventions (unpublished pilot study) and > 90 % will complete questionnaire [41, 42]. Loss to follow up after one year is expected to be 25 % according to travel patterns with high continuity of the Danes.

Multiple logistic regression analysis will be applied for analysis of differences in sunburn fraction. Analysis of variance will be used to analyze differences in sun protection score and UVR exposure score. Alpha criterion will be p=0.05 (two-tailed).

Intention-to-treat analysis will be applied by using multiple imputation by chained equations to account for missing information on sunburn among non-responders, using PROC MI in SAS 9.3. The imputation procedure includes variables hypothesized to potentially predict missing information (age, sex, education, skin type, sun behaviour, sun protection, sun intentions and intervention group). Analyses will be repeated including responders only and counting non-responders with same sunburn fraction as responders in the control group.

Clustering within families is not included in the planned analysis as it is unlikely to influence the results because participants from the same family have very low odds of being drawn with a total of 30.000 drawn out of the entire Danish population 18+ (app. 4.3 million).

Evaluation by validated questionnaire

Sun protective behavior, exposure to UVR and sunburn will be evaluated by use of a questionnaire validated by personal electronic UV-measurements [7, 43, 44]. This newly developed survey tool has made it possible in this project to evaluate the skin cancer interventions, without tracking of development of skin cancer which can take several years to develop after excessive UVR exposure. The short time period from intervention to evaluation minimizes recall bias.

Success criteria

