May-Dec 2018	Execution of interventions	Adjusting intervention groups according to participation Sending intervention packages for participants Sending questionnaires for post evaluation
Jun 2017 -Feb 2019 Jun - Nov 2019 (follow-up)	Data collection and data handling	Evaluation of participation and possible reminders Conversion of questionnaire data files for SAS and Purification of data Recording of relevant UV Indexes from vacation destinations
May-Dec 2019	1-year Follow-up	Recruitment and scheduling Sending questionnaires for evaluation
May-Aug 2019	Evaluation and documentation	Analysis and manuscript 1 (baseline)
Aug-Nov 2019		Analysis and manuscript 2 (main study)
Dec 2019 - Mar 2020		Analysis and manuscript 3 (follow-up)
Aug 2019 - Sep 2020	Dissemination of results and implementation of successful interventions	Publications in national press and international scientific papers Update of guidelines

Registering trial

The trial will be registered at clinicaltrials.gov.

Civil registry sample

The sample description of the trial to Danish health data board will be developed. Permissions will be gathered from The Danish Data Protection Agency and the National Committee of Health Research Ethics. A sample of 25.400 individuals aged 18 and older will be requested.

Study population recruitment

The study population will be recruited from the Danish Civil Registry System. The aim is to obtain a sample representing all groups of the Danish population. Recruitment for this type of trial is difficult as the target population is not easy to reach without selection bias. To improve recruitment rates invitations will be targeted to the person in the sample or to any family member in the household aged 18 and above. We aim to receive full data for a final population of approximately 2.000 persons.

It may appear, as 8 % of the original draw in the final data is not much; however, as less than half of the Danes are having vacation abroad every year it corresponds to a reach of 18 % among those eligible for the study. Alternative recruitment approaches like airport recruiting most likely would not decrease any bias or yield a higher percentage of recruited travelers. In addition, Danes also departure from nearby airports in Germany and Sweden, which would be difficult to include in the project.

Planned evaluation

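### 1,980 completers give about 89% and 60% power in four equal arms, not the stated 95% and 80%, and the 80% fails for three arms too

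*Combined protocol and SAP*

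**What the plan says.** **Sample size and power** (Statistical methods and power calculations). "The number of completing participants (n= 1.980) is based on a power calculation". The section then says that "this sample size yields 95 % probability to detect a 10-percentage point drop from 50 % to 40" per cent, "in sunburn between an intervention group and the control group", and adds "80 % probability to detect a 7-percentage point drop from 50 % to 43" per cent. The significance level is 0.05, two-tailed, and no adjustment for several comparisons is mentioned.

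**Who is counted** (Study population recruitment). "We aim to receive full data for a final population of approximately 2.000 persons".

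**Number of arms.** The Intervention study section says "we will conduct a randomized controlled trial with three arms". It then names three intervention groups (Protection Routine 1, Protection Routine 2, and the two combined) and continues: "The fourth experimental condition will be a minimal treatment control group". The Main study section also announces three groups, but control, Routine 1, Routine 2 and Routines 1 and 2 combined follow under their own headings. The distribution of participants is left to the flow diagram, which is not shown in the text available. The readable text gives no allocation ratio and no number per arm.

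**The concern.** The two power figures are the plan's quantitative justification of its sample size and its statement of the smallest effect it can detect on sunburn, the primary outcome. The comparison named is one intervention group against control, so power depends on the number per arm, and that depends on an arm count the document states inconsistently. Splitting 1,980 among the four groups described leaves about a quarter in each, which looks too few for the stated powers. The two figures also look incompatible with each other: moving from a 10-point to a 7-point drop at a fixed arm size should cost more power than the step from 95% to 80%.

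A reader who believes the 80% would take a null result as fair evidence against a 7-point benefit. The plan intends to bring effective routines into the national campaign, so that reading has consequences.

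**Working it through.** **Inputs.** From the power section: 1,980 completers; control sunburn 50%; intervention 40% or 43%; one intervention group against control; two-sided 0.05. From the Intervention study and Main study sections: four groups described, three announced. Assumed: equal allocation (relaxed in step 4).

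**Formula.** Normal approximation for two independent proportions, unpooled variance:

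SE = √[p₁(1−p₁)/n₁ + p₂(1−p₂)/n₂], power = Φ(|p₁−p₂|/SE − 1.96)

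The variance sums are 0.25 + 0.24 = 0.49 for 50% v 40%, and 0.25 + 0.2451 = 0.4951 for 50% v 43%.

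**Step 1: trying to reproduce the plan's figures with three arms.** 1,980/3 = 660 per arm.
- 10 points: SE = √(0.49/660) = 0.02725; 0.10/0.02725 = 3.670; Φ(1.710) = 95.6%. This matches the stated 95%.
- 7 points: SE = √(0.4951/660) = 0.02739; 0.07/0.02739 = 2.556; Φ(0.596) = 72.4%. The stated 80% is not reproduced.

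**Step 2: the four groups described.** 1,980/4 = 495 per arm.
- 10 points: SE = √(0.49/495) = 0.03146; 0.10/0.03146 = 3.178; Φ(1.218) = 88.8%.
- 7 points: SE = √(0.4951/495) = 0.03163; 0.07/0.03163 = 2.213; Φ(0.253) = 60.0%.
- With 2,000 in total (500 per arm): 89.1% and 60.4%.
- Detectable drop from 50% with 495 per arm: 8.8 points at 80% power, 11.3 points at 95%.

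The choice of formula does not matter. At 495 per arm, pooled variance gives 88.7% and 59.8%, arcsine 88.6% and 59.9%, and continuity correction 87.4% and 57.3%.

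**Step 3: do the two stated powers fit one arm size?** n per arm = (1.960 + z)² × variance sum / difference².
- 95% at 10 points: (1.960 + 1.645)² × 0.49/0.01 ≈ 637. That size gives only 71% at 7 points.
- 80% at 7 points: (1.960 + 0.842)² × 0.4951/0.0049 ≈ 793. That size gives 98% at 10 points.

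No common arm size yields both. Meeting both in four equal arms needs about 4 × 793 = 3,172 completers.

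**Step 4: unequal allocation.** With a control group of c and k intervention arms, the smallest intervention arm has at most (1,980 − c)/k people, and power rises with arm size. Maximising over c bounds the power of the least-powered intervention arm:

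| Arms | 50% v 40% | 50% v 43% |
|---|---|---|
| Stated | 95% | 80% |
| Four, equal (495) | 88.8% | 60.0% |
| Four, upper bound (c = 734; 729) | 91.0% | 63.1% |
| Three, equal (660) | 95.6% | 72.4% |
| Three, upper bound (c = 830; 825) | 96.2% | 73.7% |

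**Step 5: where the figures may come from.** This is inference. With continuity correction, 95% power for 10 points needs 661 per arm, or 1,983 in three arms, close to 1,980. The 80% appears at 660 per arm only with a one-sided 5% test (81.8%; 80.3% with continuity correction), which contradicts the stated two-tailed level. With four arms a one-sided test still gives only about 71%.

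**The case against.** **1,980 may already exclude non-users.** The plan's recruitment assumptions multiply to 0.25 × 0.80 × 0.90 = 18%, the same as the reach among eligible people quoted under Study population recruitment. The 0.80 is use of the intervention. Since an intention-to-treat analysis with imputation is planned, more people might be analysed:
- Responders would number 1,980/0.80 = 2,475, about 619 per arm in four arms: 94.5% and 69.7%.
- Randomised participants would number 1,980/(0.80 × 0.90) = 2,750, about 688 per arm: 96.3% and 74.2%.

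This deserves weight: on that reading the 10-point figure is close to 95%. However, the plan attaches its power to the 1,980, the recruitment section describes about 2,000 as people with full data, and the figures above ignore dilution by non-users. If non-users gained nothing, a 10-point effect would shrink to 0.8 × 10 = 8 points, and 619 per arm would give about 81%. In four arms the 7-point figure stays below 80% throughout. It passes 80% only by combining this reading with three arms and no dilution: 2,475/3 = 825 per arm gives 81.5%, but then 98.4% for 10 points, so the stated pair is still not reproduced.

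**The missing diagram might show unequal arms.** The bound in step 4 concerns the least-powered arm, so one favoured arm could do better. With 793 in control and 793 in one intervention arm, that arm reaches 80% for 7 points. But (1,980 − 1,586)/2 = 197 then remain in each other intervention arm, with about 43% power. The diagram could rescue the claim for one routine, not for all three.

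**A different comparison may have been meant.** The success criterion speaks of intervention groups in the plural. Pooled interventions against control give 97.2% and 77.2% with four equal arms (1,485 v 495), and 98.8% and 83.8% with three (1,320 v 660). A 990 v 990 comparison gives 99.4% and 87.9%. Some of these exceed 80%, but none is the comparison the power section names, and none gives 95% and 80% together.

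**The consequences are modest.** The 10-point drop is the main target and its power remains reasonable, and all four groups are clearly described despite the miscount. Both points stand. They limit the practical damage but do not make the stated figures correct.

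**Conclusion.** The concern holds. For the comparison, alpha and number of completers that the plan states, the 80% for a 7-point drop is wrong whether there are three arms (72%) or four (60%). The 95% for a 10-point drop is right for three arms and overstated for the four groups described (89%).

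The point values assume equal allocation and 1,980 as the number with outcome data. Without equal allocation, the least-powered intervention group still cannot exceed 91% and 63% in four arms, or 96% and 74% in three. The 10-point shortfall is the less certain part, because it nearly disappears if 1,980 excludes non-users and their dilution is ignored. The 7-point shortfall in four arms survives every reading of the 1,980 considered. No allowance was made for testing three routines. A Bonferroni split over three comparisons would lower four-arm power further, to about 78% and 43%.

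**What to change.** 1. State four arms consistently in the Intervention study and Main study sections.
2. Give in the text the number of completers planned per arm in the flow diagram, and say whether the 1,980 counts everyone with outcome data or only those who used the intervention.
3. Restate the power for that number per arm. With equal allocation the statement would be: 495 completers per arm give about 89% power for a drop from 50% to 40%, about 60% for a drop from 50% to 43%, and 80% for a drop of about 8.8 points, for each intervention group against control at two-sided 0.05.

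This changes wording only; participants, arms and analysis stay as they are. The cost is a less favourable power statement, mainly for the 7-point drop.

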majority of the elements in intervention 1. The feasibility of intervention 2 was previously shown [42, 61]. Ninety-three percent received and read the material. At posttest, we showed a sunburn rate in the study population, which was 17 percentage points lower than reported for our annual survey of the Danish population. All intervention elements (Sun advice, smartphone application, sunscreen application guide, skin type guide) proposed in this study were considered relevant and useful by more than 80 % of those who completed the pilot study. The skin type guide scored lowest with 81 % and the app scored highest with 95 % among those who had it available (google android and apple ios phones; not available for windows phones for instance). Furthermore, we saw a 9-percentage point increase in use of sunscreen, while use of long-sleeves and hat was largely unchanged. The hats proposed for the study, were not tested in the pilot, however the feasibility of the hat was previously tested in minor interventions. We also show a slight increase in knowledge of the UV Index in the population survey from 89 % to 93 % in the pilot test.

Potential pitfalls

Albeit highly unlikely, we have sketched various scenarios that could influence the project.

The project is based in the Danish Cancer Society, which means that during the project period, should any of the applicants change job, be long term absent/sick or likewise, qualified researchers of same level will replace them.

The project involves products from third part companies, which can be prone to internal or external structural changes or bankruptcy, leaving them no possibility to deliver a given product. In any case, an equally qualified product will be sought in replacement.

The recruitment method is register based. Should the Danish Civil Registry for some reason not be able to deliver data, like sudden legal changes in person data handling or likewise, other methods of recruitment are available.

All potential changes to the project will of course be reported to funder immediately.

Protocol

Time Schedule

Mar-Apr 2018	Planning of intervention & evaluation	Registering trial Ordering sample from civil registry system Preparation of interventions Preparation of information and homepage
Apr-May 2018	Recruitment and scheduling;	Sending invitations Ordering products for intervention Baseline Questionnaire

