The evaluation will be conducted in the online survey system, SurveyXact, provided by Rambøll. The system is used in numerous evaluations of the Danish Cancer Society. The evaluation is based on the validated UV behavior questionnaire recently developed by Danish Sun Safety Campaign. The questionnaire will be adapted to the trial.

[figure not shown]
Preparation of interventions

An intensive intervention package was developed prior to the study. The package is composed by known elements from the Danish Sun Safety campaign. The package also includes download of the UV-App developed by the Danish Sun Safety Campaign. The app includes an alert function for high UV-Indexes and can be adapted to the correct location by GPS or a selected city around the world. This mobile app is fully developed and available for this trial. The participants randomized to the package will receive alerts to take precautions against solar UVR before and during their vacation.

Invitations

The invitations for the project will be handled (printed, enveloped and sent) by trained volunteers from the Danish Cancer Society. Participants will sign up for the project on a developed web-page of the project. On the project homepage the participants will fill in a short form of contact information, demographic information, departure and arrival dates of their upcoming vacation and baseline sun behavior information for non-responder analyses. Participants who have not yet planned their vacation are instructed to contact the project team

Flow Diagram

once they have planned it. Likewise they will be reminded every 2-3 weeks during the period by mail or phone. Repeated invitations will be sent after two and four weeks to non-responders. Afterwards, participants will be contacted by the volunteers by phone to confirm their participation and receive information about the study. A student will be dedicated in organizing workflow of the volunteers and participate in the training of the volunteers. We have good experiences with this procedure from other projects like www.mituv.dk and www.statusd.dk also funded by TrygFonden.

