Invitations will be identical for all invited potential participants. It will include invitation to participate in a project about how the Danish Cancer Society can improve their knowledge about sun protection information and that they will be allocated to use a specific sun protection during their vacation. It will also include information about which procedures may be applied.

Recruitment

The invited participants will provide their contact data and supplemental background data upon recruitment on the project homepage. Only one person from a family will be enrolled in the study.

Development of protection routines and training package intervention

The final information package is composed by various elements from the Danish Sun Safety campaign as described in the project description. The package was created by an experienced group from the Danish Sun Safety Campaign, including experts in public health, anthropology and communication and was be piloted before the trial.

Main study

The participants will be randomized to one of the three groups below after agreeing to participate. The detailed distribution of participants are shown in the flow diagram. The randomization will be stratified by gender (Male/Female), age group (18-25, 26-35, 36-45, 46-55, 56-65 and 65+) and region (Capital, Zealand, Northern Jutland, Central Jutland and Southern Denmark). The randomization procedure will be blind to the researcher. All participants will be contacted immediately before their vacation and will receive their intervention package before departure.

Control group – Minimal intervention

All groups including the control group will receive a minimal intervention with the sun advice from the Danish Sun Safety Campaign.

Protection Routine 1 – Intensive information and training in current sun advice

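### The model for the sun protection and UVR exposure scores names no stratification or baseline term; run on arm alone it is valid but gives up some precision that could be had almost free

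*Combined protocol and SAP*

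**What the plan says.** All references are to the combined protocol and SAP.

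- **Score analysis** (Statistical methods and power calculations): "Analysis of variance will be used to analyze differences in sun protection score and UVR exposure score". No covariate is named. The sentence before it gives sunburn a multiple logistic regression.
- **Allocation** (Main study): "The randomization will be stratified by gender (Male/Female), age group (18-25, 26-35, 36-45, 46-55, 56-65 and 65+) and region". There are five regions.
- **Timing of baseline data** (Intervention study): "After enrollment and pretesting, participants will be randomly assigned". The Time Schedule places a baseline questionnaire in the recruitment period, April to May 2018.
- **Stated use of baseline data** (Invitations): the sign-up form collects "baseline sun behavior information for non-responder analyses".
- **Imputation** (Statistical methods and power calculations): multiple imputation is used "to account for missing information on sunburn among non-responders", with predictors "age, sex, education, skin type, sun behaviour, sun protection, sun intentions and intervention group".
- **Possible confounders** (Confounders): the list has age, gender and sun-seeking behaviour among others. Region is not on it, and no model is mentioned.
- **Other adjustment** (Potential bias): the questionnaire is said to permit adjustment for UV exposure received, in responder analyses.

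**The concern.** Two kinds of pre-randomisation information are available and neither is assigned to the score comparison. The first is the stratification factors, which must be known for every participant at allocation. Stratifying balances them across arms, but an analysis that leaves them out keeps their variance in the error term. The standard error is then slightly too large and the test slightly conservative. The second is the baseline sun-behaviour information, whose stated purpose is the non-responder analyses.

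What is at stake is precision only. If the scores are compared on arm alone, confidence intervals will be somewhat wider than they need to be. Treatment effects are not biased and the type I error is not inflated.

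A second, smaller matter is that the model is left open. The covariates could be chosen after the data are seen. The only adjustment tied to a set of analyses is for UV exposure received, which is measured after randomisation and may itself be changed by the interventions. For the UVR exposure score, that covariate would come close to being the outcome.

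**Working it through.** **No figure to reproduce.** The plan's power statements concern sunburn. It gives no standard deviation, target difference, power or baseline correlation for either score. The calculation below therefore shows how the gain depends on an assumed correlation.

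**Inputs from the documents.** 1,980 completers; two-sided alpha of 0.05; strata of gender (2 levels), age group (6) and region (5).

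**Assumptions.** Score SD of 1; four equal arms of 1,980 / 4 = 495, because the Intervention study section mentions both three arms and a fourth condition and the flow diagram is not shown; comparison of two arms with 80% power before adjustment; baseline-outcome correlation rho of 0.1 to 0.3.

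**Step 1: cost of the extra terms.** Gender 1 + age group 5 + region 4 + baseline measure 1 = 11 parameters. With covariates that are not balanced by design, the expected inflation of the standard error is

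sqrt(1 + 11 / (1980 − 4 − 11 − 1)) = sqrt(1 + 11/1964) = 1.0028, or about 0.3%.

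This is an upper figure. A simulation with permuted blocks of 4 within 60 strata (an assumption, since the block method is not stated) gave a cost of about 0.03%, because the strata are already balanced.

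**Step 2: net gain.** Standard error factor = sqrt(1 − rho²) × 1.0028. Extra participants of equal worth = 1980 × (1/factor² − 1). Power is from the noncentral t distribution.

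| rho (assumed) | SE factor | Fall in SE | Power, from 80% | Equivalent extra participants | Detectable difference at 80% power (0.178 SD unadjusted) |
|---|---|---|---|---|---|
| 0.1 | 0.9978 | 0.2% | 80.2% | 9 | 0.178 SD |
| 0.2 | 0.9825 | 1.7% | 81.4% | 71 | 0.175 SD |
| 0.3 | 0.9566 | 4.3% | 83.4% | 184 | 0.170 SD |

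With three arms of 660 the percentages are the same. The detectable difference starts at 0.154 SD and becomes 0.152 SD at rho 0.2 and 0.148 SD at rho 0.3.

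**Step 3: break-even.** The gain offsets the 0.28% cost when rho = sqrt(1 − 1/1.0028²) = 0.075. With the simulated cost of 0.03% it is sqrt(1 − 1/1.0003²), about 0.025.

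**Step 4: higher correlations.** At rho 0.5 the factor is sqrt(0.75) × 1.0028 = 0.868, a fall of 13% worth about 645 participants. Nothing in the documents supports a value that high. The Data collection and handling section reports that answers were valid within two weeks of return, and a baseline recall of an earlier vacation would normally fall outside that window.

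**Step 5: region alone.** Region is the one stratification factor that the plan lists nowhere as a possible covariate. If it explains a share R² of the score variance, omitting it overstates the standard error by 1/sqrt(1 − R²) − 1. That is 0.25%, 0.50% and 1.0% for R² of 0.5%, 1% and 2%. The type I error of the unadjusted two-arm test would then be 4.94%, 4.89% and 4.77%, on the conservative side of 5%.

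**The case against.** The strongest reply is that silence is not exclusion. The plan names a family of methods in one sentence and does not say one-way or unadjusted. Analysis of variance can carry gender, age group and region as factors. The Confounders section comes directly before the statistical methods and already names two of the three stratification factors and a behaviour measure. This stands. A reader might infer that the plan commits to an unadjusted comparison; the documents do not establish that, so the precision loss is conditional on the scores being analysed on arm alone. What survives is that no adjustment is specified and that region appears nowhere as a covariate.

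A second reply is that the baseline term may be weak or missing. This stands in part. The presence of sun protection among the imputation predictors suggests a related baseline measure. However, the content of the pretest is not described, and no section says that either score is computed at baseline. The UVR exposure score for the trial vacation has no evident pre-vacation counterpart. The gain from a baseline term is therefore assumed, and could be negligible.

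A third reply concerns the status of the outcomes. The Intervention study section lists "use of shade, hats, protective clothing, and sunscreen as secondary outcomes" and names neither score. A reader might take the scores to be designated secondary outcomes. The sun protection score plausibly summarises those behaviours, but the plan does not say so.

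**Conclusion.** The point holds as a low-severity matter of efficiency and specification. The plan names no covariate for the two scores although the stratification factors and baseline sun behaviour will be in hand. If the analysis is run on arm alone, it remains valid and errs slightly on the conservative side.

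The size of the loss cannot be derived from the documents. The falls of 0.2%, 1.7% and 4.3% in the standard error rest on assumed correlations of 0.1, 0.2 and 0.3 and on 1,980 completers in equal arms; the loss would be larger at higher correlations. Two stronger inferences should be avoided. One is that the planned comparison is biased or has an inflated error rate, which it does not. The other is that a material loss of power has been shown, which would need a correlation that the documents do not report.

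**What to change.** State in the SAP that each score will be analysed by ANCOVA with terms for arm, gender, age group, region and one pre-specified sun-behaviour or sun-protection measure already collected before randomisation. Name that measure. State also that no post-randomisation covariate, such as UV exposure received, enters these comparisons.

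The cost is SAP wording. No new data, contact or participant is needed. The model uses 11 further parameters among about 1,980 participants, at most about 0.3% on the standard error and probably nearer 0.03% if allocation is in blocks within strata.
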